7.5.2 Bleeding Score - SMOG

Bleeding, as measured by ITP-BAT SMOG, will be listed for all treated subjects. Due to the nature of the incremental assessment of ITP-BAT, evaluation period (start day and end day) will be provided. Start day of an assessment is the end day of the immediately previous assessment visit. Start day would be missing for the first bleeding assessment (screening visit).

7.5.3 Platelet Count

Bleeding SMOG score, platelet count, platelet change from baseline, potentially rescue medication flag, and response category (each under primary and secondary efficacy criteria) at each study day will be listed for all treated subjects.

Platelet count and change from line will be summarized by treatment group for each study day. Percent of visits with platelet count $\geq 30,000/\text{mm}^3$, $50,000/\text{mm}^3$, and $100,000/\text{mm}^3$ will be listed for each subject and summarized for each treatment group.

Platelet count and its change from baseline may be explored by graphs and statistical models. Details are available in the section of exploratory biomarker analysis.

Exploratory analysis of platelet count is shown in section 0.

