3 INVESTIGATIONAL PLAN

3.1 Study Design and Duration

This is a Phase 1b/2, multicenter, open-label study to evaluate the safety, efficacy, dose response, and pharmacology (PK, target engagement and PD) of BMS-986004 in subjects with ITP.

The study will comprise a short-term period and a long term extension (LTE) period.

The short-term period, is divided into three phases: Response Phase (6 weeks), Remission Phase (6 weeks) and Follow Up phase (8 weeks).

Screening evaluations to determine subject eligibility will be performed 21 days prior to study drug administration. The screening period may exceed 21 days but not more than 42 days total, and only after a discussion with and approval by the Study Director. If an extension in screening time is granted, the patient must still follow the platelet count rules for enrollment. The baseline platelet count determining enrollment eligibility will be based on the mean of two determinations taken within a week of the first dose. To be eligible for enrollment, platelet count needs to be less than $30,000/\text{mm}^3$ and show stable or declining trend. If the mean platelet count is between $30,000 - 35,000/\text{mm}^3$ the subject may be considered for enrollment on a case by case basis after discussion with and approval by the Study Director.

Following screening, a total of 40 evaluable subjects are planned for the study. Subjects are considered evaluable if they receive the first 4 doses of study drug and complete the required

safety and efficacy evaluations at Day 50. Non-evaluable subjects will be replaced to maintain a count of 10 subjects in each dose panels, except subjects will not be replaced if they are discontinued from the study secondary to an adverse event unless the adverse event can be determined to be unrelated to treatment.

Subjects are treated in dose panels of 10 subjects each. Four (4) dose panels are planned to be enrolled sequentially in an ascending manner, with dose intensity selected to provide increased levels of immunosuppression at steady state. Dose levels (range from 75 mg to 1500 mg administered every two weeks) that are planned to be evaluated in this trial are expected to elicit a range of clinical response.

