3.3.1 Inclusion Criteria

1. Signed Written Informed Consent

- a) The signed written informed consent form must be obtained from the subject in accordance with requirement of the study center's IRB, prior to initiation of any protocol required procedures.

2. Target Population

- a) Adults (≥ 18 years old), diagnosed with persistent or chronic ITP according to American Society of Hematology (ASH)/British Committee for Standards in Haematology (BCSH) guidelines, with or without prior splenectomy.
- b) Subjects previously received one or more prior ITP therapies and must have had initially responded to at least one prior ITP therapy. Previous treatments for ITP include but are not limited to TPO mimetics/agonists, corticosteroids, immunoglobulins, azathioprine, danazol, cyclophosphamide and/or rituximab.
- c) Subjects have had relapsed ITP i.e. failed to achieve a sustained (for more than 3 month) platelet count $\geq 50,000/\text{mm}^3$ to at least one prior ITP therapy.
- d) The platelet count (calculated from the mean of the 2 counts taken within a week of the first dose, during the screening and pre-treatment periods) must be less than $30,000/\text{mm}^3$ with no count greater than $35,000/\text{mm}^3$. If the mean of the counts is between $30,000$ - $35,000/\text{mm}^3$, the subject may still be eligible but enrollment will be on a case by case basis and require approval by the Study Director.
- e) Subject Re-enrollment: This study permits the re-enrollment of a subject that has discontinued the study as a pre-treatment failure (ie, subject has not been randomized / has not been treated). If re-enrolled, the subject must be re-consented.
- f) A complete blood count must be within the reference range (including white blood count [WBC] differential not indicative of a disorder other than ITP), with the following exceptions:
 - i) subjects with hemoglobin levels between 9 g/dL for females and 10 g/dL for males and the lower limit of normal (LLN) are eligible for inclusion, if anemia was clearly attributable to ITP (excessive blood loss);
 - ii) absolute neutrophil count (ANC) greater than or equal to $1500/\mu\text{L}$ (elevated WBC/ANC due to corticosteroid treatment is acceptable)
- g) Prothrombin Time/International Normalized Ratio (PT/INR) and activated partial thromboplastin time (aPTT) must have been within 80% to 120% of the normal range with no known hypercoagulable state.

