Plasma Soluble Free CD40L Level			X	See Section 5.6
Plasma Soluble Total CD40L Level			X	See Section 5.6
Platelet-Associated Anti-platelet Antibodies (WB)		X		See Section 5.6
Platelet Ag-specific B cells by ELISPOT assay (WB)		X		See Section 5.6
B cell Repertoire Analysis (WB)	X		X	See Section 5.6
Immune Cell Counts (T, B, and NK) and Phenotypes (WB)		X		See Section 5.6
Adverse Event Reporting				
Monitor for Serious Adverse Events	X	X	X	All SAEs must be collected that occur during the screening period and within 3 months of discontinuation of dosing.

Table 5.1-2: On Treatment Procedural Outline (IM140103)

Procedure	D 1	D 2	D 4	D 8	D 15	D 29	D 43	D 50	D 57	D 71	D 72, 75, and 78	D 85 / ET	FU1 (D99) ^a	FU2 (D113) ^a	FU3 (D127) ^a	FU4 (D141) ^a	Notes	
Safety Assessments																		
Physical Examination (PE)	X											X						
Physical Measurements	X				X	X	X		X	X		X	X	X		X	Weight only	
Vital Signs	X	X	X	X	X	X	X		X	X		X	X	X	X	X	See note in screening procedures.	
Electrocardiogram (ECGs)	X									X		X					See note in screening procedures.	
Laboratory Tests	X	X	X	X	X	X	X	X	X	X	X	X	X	X	X	X	See note in screening procedures and Section 5.3.2 . Pre-dose on Day 1. Platelet count included in this test as an efficacy parameter. (Hematology, Serum Chemistry, and Urinalysis)	
Pregnancy Test	X								X	X		X	X	X		X	For women only (urine or serum)	
ITP-BAT (SMOG Score)	X	X	X	X	X	X	X	X	X	X	X	X	X	X	X	X	Subjects will be graded according to the ITP-BAT - Bleeding Assessment Tool	
Adverse Event Reporting																		
Monitor for Non-Serious Adverse Events	X	X	X	X	X	X	X	X	X	X	X	X	X	X	X	X		
Monitor for	X	X	X	X	X	X	X	X	X	X	X	X	X	X	X	X	X	See note in screening

Table 5.1-2: On Treatment Procedural Outline (IM140103)

Procedure	D 1	D 2	D 4	D 8	D 15	D 29	D 43	D 50	D 57	D 71	D 72, 75, and 78	D 85 / ET	FU1 (D99) ^a	FU2 (D113) ^a	FU3 (D127) ^a	FU4 (D141) ^a	Notes
Serious Adverse Events																	procedures.
Pharmacokinetic (PK) Assessments																	
Serial Blood PK Sampling	X	X	X	X	X	X	X	X	X	X	X	X	X	X	X	X	See Section 5.5 .
Immunogenicity Sampling	X				X	X	X		X	X		X	X	X	X	X	See Section 5.5
Exploratory PD Biomarker Assessments																	
CD40L Receptor Occupancy (WB)	X	X			X		X			X		X	X	X	X	X	See Section 5.6 . On Dosing days Receptor Occupancy samples must be collected prior to dosing.
Whole Blood Gene Expression				X		X			X		X*			X	X		See Section 5.6. (* day 78 only)
Plasma Soluble Free CD40L Level				X		X			X	X		X	X	X	X	X	See Section 5.6.

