5.4.2 Secondary Efficacy Assessments

- Proportion of subjects achieving platelet count $\geq 50,000/\text{mm}^3$ with an increase of at least $20,000/\text{mm}^3$ from Short Term Day 1 and absence of bleeding
- Percent of visits with platelet count above $30,000/\text{mm}^3$ ($50,000/\text{mm}^3$ or $100,000/\text{mm}^3$). If subject entered study with baseline between $30,000\text{-}35,000/\text{mm}^3$ at Short Term Day 1,

determine percent of visits with platelet count above subject's Short Term Day 1 platelet count.

- Mean platelet count at each visit
- Mean change from baseline in platelet counts at each visit
- Mean fold change from baseline in platelet counts at each visit
- Time to response: time from starting treatment to achievement of CR or R.
- No response (NR): platelet count $< 30,000/\text{mm}^3$ or less than 2-fold increase of baseline platelet count or bleeding.
- Percentage of participants experiencing any bleeding episode and the total number of bleeding events.
- Subject's Bleeding Score (measured by the ITP-BAT Bleeding Assessment Test)
- Corticosteroid-dependence - the need for ongoing or repeated doses administration of corticosteroids for at least 2 months to maintain a platelet count at or above $30,000/\text{mm}^3$ and/or to avoid bleeding.
- The duration of response is measured from the achievement of a first measured CR or R until the loss of CR or R.
- Ability to maintain Response or Complete Response after stopping treatment.

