7.5.1 Derivation of Efficacy Endpoints

Primary efficacy criteria and response category:

- Response (R) - platelet count $\geq 30,000/\text{mm}^3$ and at least 2-fold increase from the baseline count and absence of bleeding.
- Complete Response (CR) - platelet count $\geq 100,000/\text{mm}^3$ and absence of bleeding.
- No Response (NR) - platelet count $< 30,000/\text{mm}^3$ or less than 2-fold increase of baseline platelet count or bleeding.
- Not Assessable (NA) - platelet count is missing or is excluded due to rescue medication.

Subject's best response is decided in the order of CR, R, NR, and NA.

Secondary efficacy criteria and response category:

- Clinically Significant Response - platelet count $\geq 50,000/\text{mm}^3$ with an increase of at least $20,000/\text{mm}^3$ from baseline and absence of bleeding.
- No Clinically Significant Response - platelet count $< 50,000/\text{mm}^3$, or increase of $\leq 20,000/\text{mm}^3$ from baseline, or bleeding.
- Not Assessable (NA) - platelet count is missing or is excluded due to rescue medication.

Absence of bleeding:

Absence of bleeding is defined as SMOG scores being zero for all the three major domains (Skin, visible mucosae, and organs) with ITP-BAT on the same day when platelet count is assessed.

Platelet data exclusion and rescue medication flag:

Platelet counts collected within 4 weeks after any rescue medication, though still shown in listing of figures of raw data, will be excluded from summarizing platelet and deriving subject response. To facilitate the exclusion, rescue medication flag may be derived and included in some analysis datasets and listings if at least one subject takes rescue medication after the first dosing during the trial. Rescue medication flag is set to Y (Yes) within 4 weeks after the day any rescue medication is administered, i.e., between rescue medication day and rescue medication day + 27, inclusively. It will be set to N (No) when otherwise.

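### SAP 7.5.3 lacks the protocol's own-Day-1 rule for subjects entering at 30,000–35,000/mm³, so the share of visits meeting the 30,000 cut-off runs high for them

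*SAP*

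**What the plan says.** Protocol 5.4.2 (Secondary Efficacy Assessments) includes the measure "Percent of visits with platelet count above" 30,000/mm³, with 50,000 and 100,000/mm³ as further cut-offs. For subjects whose Short Term Day 1 baseline lies between 30,000 and 35,000/mm³ it adds a special instruction: "determine percent of visits with platelet count above subject's Short Term Day 1 platelet count".

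SAP 7.5.3 (Platelet Count) defines the same measure with cut-offs of ≥30,000, 50,000 and 100,000/mm³. The percentages "will be listed for each subject and summarized for each treatment group", with no condition on baseline. The visible endpoint definitions in SAP 4.1 and the derivations in SAP 7.5.1 do not supply the rule either.

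Subjects in this band can enter. Inclusion criterion 2d in protocol 3.3.1 asks for a mean below 30,000/mm³, but between 30,000 and 35,000/mm³ "the subject may still be eligible but enrollment will be on a case by case basis and require approval by the Study Director".

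SAP 2.4 says the plan reflects the protocol through Amendment 02. SAP 7.2 undertakes that changes from the protocol's planned analyses will be defined in the SAP and reported in the CSR.

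**The concern.** A subject who enters at 30,000–35,000/mm³ meets the SAP's lowest cut-off before receiving any drug. The protocol anticipated this and moved the comparator to the subject's own Day 1 count. A programmer following the SAP as written would instead credit such a subject with visits that show no improvement. A subject whose usual level is 15,000/mm³ would score close to zero without a drug effect, so one panel summary would combine subjects with very different no-effect values. Panels hold only 10 subjects, and describing dose response by platelet count is a secondary objective, so one or two such subjects in a panel could visibly move its figure.

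**Working it through.** The documents give no figure for this measure, so there is none to reproduce. The only stated precision figure is the 90% interval for 4 responders out of 10 in protocol 8.1. It reproduces as an exact Clopper–Pearson interval (0.150 to 0.696), but it concerns response rate and has no bearing here.

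**Inputs from the documents.** The cut-offs and the Day 1 rule come from protocol 5.4.2 and SAP 7.5.3. The entry band comes from protocol 3.3.1, and the panel size of 10 from protocol 3.1. Table 5.1-2 has a platelet count at every visit ("Platelet count included in this test as an efficacy parameter"), which gives 17 short-term visits after dosing starts: Days 2, 4, 8, 15, 29, 43, 50, 57, 71, 72, 75, 78, 85, 99, 113, 127 and 141.

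**Assumed, not in the documents.** Counts are log-normal around the subject's usual level, with a within-subject CV of 10%, 20% or 30%. The log SD is s = √ln(1 + CV²) = 0.100, 0.198 or 0.294.

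**Step 1: direction.** Let D be the Day 1 count, with D ≥ 30,000. Every visit above D is also at or above 30,000, so for such a subject the SAP percentage can never be below the protocol's. The gap is exactly the share of visits with a count from 30,000 up to and including D. It vanishes for a subject whose counts all rise above D.

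**Step 2: chance of scoring a visit with no drug effect.** For usual level b, P(count ≥ 30,000) = Φ(ln(b/30,000)/s). For example, b = 32,500 and CV 20% give Φ(0.0800/0.198) = Φ(0.404) = 0.66.

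| Usual level (/mm³) | CV 10% | CV 20% | CV 30% |
|---|---|---|---|
| 30,000 | 50% | 50% | 50% |
| 32,500 | 79% | 66% | 61% |
| 35,000 | 94% | 78% | 70% |
| Average over the band, SAP rule | 76% | 65% | 60% |
| Same subjects, protocol rule | 48% | 49% | 49% |

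The first four rows come from the formula. The last row is a simulation: usual levels uniform over 30,000–35,000, two noisy pre-treatment counts, the entry limits applied, the second count taken as Day 1, then 17 visits. In that simulation the SAP rule gives 75.6%, 65.0% and 60.4%, against 48.1%, 48.8% and 49.0% under the protocol rule.

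**Step 3: effect on a panel mean.** Per affected subject in a panel of 10:
- CV 10%: (75.6 − 48.1)/10 = 2.8 points
- CV 20%: (65.0 − 48.8)/10 = 1.6 points
- CV 30%: (60.4 − 49.0)/10 = 1.1 points
- Count constant at the Day 1 value: (100 − 0)/10 = 10 points

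**Step 4: if Day 1 is a chance high.** With a usual level of 25,000–29,000/mm³ the SAP rule scores only 3–45% of visits (CV 10–30%). A further simulation drew usual levels from an assumed population with median 18,000/mm³ and between-subject CV 50%, then applied the entry limits. It gave 65/52/46% under the SAP against 41/38/37% under the protocol rule. The SAP figure is still higher, as Step 1 requires, but it is not always above 50%.

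**Step 5: other cut-offs and endpoints.** At a usual level of 32,500 the 50,000 cut-off is met at 0/1.5/7% of visits and the 100,000 cut-off at about 0%. R requires "at least 2-fold increase from the baseline count and absence of bleeding", which from 30,000–35,000 means 60,000–70,000/mm³. CR requires at least 100,000. Clinically significant response requires at least 50,000 and a rise of 20,000, so 50,000–55,000 from this band. None of these uses the missing rule.

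**The case against.** A reader might infer that the SAP removed a protocol rule without saying so. The documents do not show that. The SAP follows Amendment 02, has no long-term extension, and has a 4-week follow-up where the current protocol has 8 weeks. The rule's reference to a Short Term Day 1 is wording that fits a protocol with an extension, so it may have been added or reworded after the SAP. The date cannot be established. What can be said is that the two documents now differ.

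A reader might also infer that such a subject would score most visits as success without any drug effect. That holds only if the baseline is close to the usual level. Protocol 3.1 wants counts that "show stable or declining trend", and a count just over the usual entry limit is open to regression to the mean. Step 4 shows shares below 50%.

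A third tempting inference is that dose comparisons are distorted. No test or formal between-dose comparison of this measure is planned, and it is not among the endpoints in protocol 8.3.2 or SAP 4.1. Entry in this band is case by case, so the number affected may be zero. SAP 7.5.3 also lists each subject's counts and changes from baseline, so an affected subject would be visible.

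Two further limits stand. The protocol's rule still credits about half of visits by chance, so it reduces the artefact without removing it. Parts of the SAP are redacted and table details are deferred to a data presentation plan, so the rule is known to be absent only from the visible text.

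These points limit the size and the explanation. They do not reconcile the two definitions.

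**Conclusion.** The point holds as a minor misalignment. As written, SAP 7.5.3 would compute the 30,000 measure differently from protocol 5.4.2 for subjects entering at 30,000–35,000/mm³, and the result could only be equal or higher. The direction needs no modelling assumption. The size does: an excess of about 11–28 percentage points per affected subject rests on counts staying around baseline, no drug effect and an assumed CV of 10–30%. The share scored can fall below half if the usual level is lower than baseline. The documents do not support reading this as a deliberate departure or as a threat to the trial's efficacy conclusions. It touches one cut-off of one descriptive secondary measure.

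**What to change.** Add one sentence to SAP 7.5.3: for subjects with a Short Term Day 1 count of 30,000–35,000/mm³, the 30,000 cut-off is replaced by a count above the subject's Short Term Day 1 platelet count. Name the Day 1 count rather than writing baseline, because the eligibility baseline in protocol 3.1 is a mean of two counts, while the laboratory baseline in SAP 7.6 is the last value before dosing. State that only the 30,000 cut-off is replaced, since protocol 5.4.2 does not say which of the three it means.

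Flag these subjects in the listing, and settle whether a count of exactly 30,000 qualifies: the protocol says *above*, the SAP says ≥. If the sponsor prefers the fixed cut-off for everyone, the SAP should declare that change, as SAP 7.2 requires. The cost is a sentence or two, a flag and about one line of derivation code, with no new data.

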7.5.4 Response with primary efficacy criteria

The best response status over the entire study will be reported for all treated subjects with platelet at baseline, administered dose on day 1, and administered dose on day 57. For responders, treatment group, dose escalation status (Y/N), time to respond, time to peak response, and duration of response will be provided in a listing.

Response rates and number of subjects having dose escalated will be provided for each treatment group and all.

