3.1.1 Intra-subject dose escalation

Intra-subject dose escalation could occur after the subject has completed the Response Phase of the study. The intra-subject dose escalation decision will be based on review of the safety information and platelet count after 4 weeks of treatment. The decision to escalate dose for the subject will be made after evaluating platelet count at Day 50, 7 days after the 4th dose of BMS-986004 has been administered. Subject will receive the next higher dose of BMS-986004 if clinically significant response has not been achieved based on measurement of platelet count on

the last two consecutive counts performed at Day 43 and Day 50, and a favorable safety profile is observed (see Table 3.1.1-1). Clinically significant response is defined as achieving platelet count $\geq 50,000/\text{mm}^3$ with an increase of at least $20,000/\text{mm}^3$ from baseline and absence of bleeding. Subject will then be dosed at the higher dose level for the remainder of the study (Remission Phase), receiving investigational product at that dose on Week 8, Week 10 and Week 12. Active treatment period with BMS-986004, regardless of the dose, may not exceed 12 weeks for any individual subject.

Table 3.1.1-1: Dose Adjustment after Response Phase

Platelet Count at Day 43 and Day 50 (7 days after the 4th dose) (X /mm³)	Action
< 50,000	Dose increase, as indicated by the next dose panel
$\geq 50,000$ with an increase of at least 20,000 from baseline	Dose remains constant on bi-weekly schedule

3.1.2 Dose frequency adjustment for responders exceeding 450,000/mm³ (for non-splenectomized subjects) and 600,000/mm³ (for splenectomized subjects) platelet count

For both the Short Term Study and the Long Term Extension plan, in the event that platelet count exceeds $450,000/\text{mm}^3$ for non-splenectomized subjects and $600,000/\text{mm}^3$ for subjects who underwent splenectomy, in the absence of recent (administered within two weeks) rescue medication, as indicated by the two consecutive platelet count measurements, dosing of the BMS-986004 should be stopped. Subject will remain in the study and platelet counts will be then assessed based on the normal study visit schedule. Dosing of BMS-986004 could be reinitiated only after discussion between Study Director and Investigator if clinically appropriate and dictated by the medical judgment and subject’s safety.

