- Extremely small probability for β_2 being negative

It is assumed that the response rate at dose of 75mg, 225mg, 675mg, and 1500mg to be 0.2, 0.4, 0.55 and 0.7 respectively. A linear regression using the above data will give prior mean μ to be (-1.33, 0.72) with rounding error. The second and third bullets of the guidelines would make the stand deviation of β_1 to be 0.45, and β_2 to be 0.2. Prior distributions of β_1 and β_2 are assumed to be independent. A 95% credible interval of response rates under prior and without observation data is shown in Figure 1, where the top curve is the upper 97.5% quantile, the center is the mean, and the bottom is the lower 2.5% quantile. The circles represent the expected response rates at the selected doses. It can be seen that the chosen prior would lead to a mean response rate estimate being very close to the expected or assumed, and at the same time the wide region of 95% credible interval indicates that the prior's weak impact on the posterior estimation of response rate when data are observed.

Figure 1: 95% Credible Interval of Response Rate under Prior Only

Special consideration for titration

Non-responders at each cohort other than the maximum 1500mg cohort would be administered higher dose with the hope of becoming responders. Therefore, two response status data may be observed for those non-responders. Due to relative small sample size of each cohort, making use of status data after the titration dose is believed to increase the accuracy of model-based prediction under some reasonable assumptions. Listed in the below are two assumptions used in the adaptive dose selection:

- If a subject responds to a dose, the subject would respond to higher dose with probability 1.

- If a subject does not respond to a dose after 3 administrations, additional dosing at the same dose would not make a subject change from non-responder to responder.

Based on the above assumptions, a new approach is proposed to combine the subjects at two adjacent cohorts to estimate the response rate at the higher dose which is shared by the two cohorts.

Simulation

Trial simulation is done to show the performance of logistic regression and Bayesian logistic regression with starting dose data only or with titration data included. The Settings of simulation parameters are listed below for convenience:

[figure not shown]
- Doses: 75, 225, 675, 1500
- Rate: 0.2, 0.4, 0.55, 0.7

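### Response rests on one qualifying platelet count at any visit, with no control arm, so chance inflates the rate; a confirmed response rate should be added

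*SAP*

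**What the plan says.** - **Class of each count.** SAP 7.5.1 classes every count as CR, R, NR or NA. R needs at least 30,000/mm³ and "at least 2-fold increase from the baseline count and absence of bleeding". CR needs at least 100,000/mm³ and no bleeding. "Absence of bleeding is defined as SMOG scores being zero for all the three major domains", on the day of the count. Counts within 4 weeks after rescue medication are excluded.
- **Class of the subject.** "Subject's best response is decided in the order of CR, R, NR, and NA" (SAP 7.5.1). SAP 7.5.4 adds "The best response status over the entire study will be reported for all treated subjects" and gives response rates by treatment group. SAP 7.5.5 gives rates for clinically significant response during the whole study.
- **Confirmation.** Neither document asks for a second qualifying count or a minimum duration. Protocol 5.4.1 also defines R and CR on a count, without confirmation.
- **Visits.** Protocol Table 5.1-2 has 17 platelet visits after Day 1 for subjects who do not enter the extension. SAP 2.1 has a 4-week follow-up, which leaves 15.
- **Control.** Protocol 1.2 states that there is no placebo control.
- **Two counts elsewhere.** Eligibility uses the mean of two counts (Protocol 3.3.1, criterion 2d). Intra-subject escalation uses "the last two consecutive counts performed at Day 43 and Day 50" (Protocol 3.1.1). The high-platelet rule applies "as indicated by the two consecutive platelet count measurements" (Protocol 3.1.2).

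**The concern.** A best-of-many-visits endpoint gives each subject many chances to cross the threshold. A subject whose underlying count never changes becomes a responder if one bleed-free count happens to reach 30,000 and double the baseline. Entry requires a low count, which tends to select subjects at a low point, and with no control arm the trial itself cannot show how often this happens.

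Efficacy and dose response are both secondary objectives. A chance floor acts only on subjects who do not truly respond, so it lifts the low doses most and flattens the dose response.

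**Working it through.** **1. The plan's own figure.** Protocol 8.1 gives a 90% interval of (0.15, 0.70) for 4 responders out of 10. The exact interval is the 5% quantile of Beta(4, 7), 0.150, to the 95% quantile of Beta(5, 6), 0.696, so it reproduces. It covers sampling error only, not subjects called responders by chance.

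**2. Number of chances.** Days 2, 4, 8, 15, 29, 43, 50, 57, 71, 72, 75, 78 and 85 make 13. Follow-up Days 99, 113, 127 and 141 bring this to 17. The SAP's 4-week follow-up keeps two of those four: 13 + 2 = 15.

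If visits were independent with per-visit chance q, the any-visit rate is 1 − (1 − q)^17. For q = 1%, 2% and 5% this is 15.7%, 29.1% and 58.2%. Small per-visit rates add up quickly.

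**3. Simulation with no drug effect.**
- From the documents: visit days; two pre-dose counts with mean below 30,000 and none above 35,000; R/CR as in SAP 7.5.1; baseline as the last pre-dose value (SAP 7.6).
- Assumed: true mean level log-uniform from 8,000 to 30,000; count = level × exp(sZ − s²/2) with s² = ln(1 + CV²); correlation between visits exp(−days apart/τ), with τ of 0 (independent), 7 or 28 days; each visit bleed-free with probability 1.0, 0.7 or 0.5. Rescue exclusion is not modelled.
- Confirmed rule: two qualifying counts at least 7 days apart with no failing count between them.

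| Assumed CV | Any single count, 17 visits | Confirmed |
|---|---|---|
| 20% | about 1–2% | 0–0.3% |
| 30% | 5–13% | 0.4–2.6% |
| 40% | 11–26% | 1–6% |
| 50% | 17–38% | 2–10% |

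The ends of the two ranges come from different scenarios, so they should not be paired. Paired results at CV 40% are:
- independent counts, always bleed-free: 26% falls to 3%;
- τ = 28 days, always bleed-free: 16% falls to 6%;
- τ = 28 days, half of visits bleed-free: 11% falls to 2%.

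The confirmed rule removes more than half of the chance responders in every scenario run. The table is for R/CR. The clinically significant criterion is harder to meet by chance: about 3–8% at any visit at CV 40% in the same model.

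**4. Sensitivity to the model.** Taking the assumed level as the median instead of the mean, with independent bleed-free counts, gives 2.5%, 14%, 29% and 43% at the four CVs. Using the mean of the two pre-dose counts as baseline in that case gives 1.2%, 12.5%, 29.5% and 45.3%. A separate model (log-normal levels with median 12,000, between-subject log SD 0.4, within-subject log SD 0.4, τ = 7 days, no bleeding) gives 17.7% over 17 visits, 15.9% over 15, 8.0% over the 7 visits to Day 50, and 4.0% for two consecutive qualifying visits.

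**5. Effect on the trial.** In a cohort of 10 true non-responders, a floor of 5–13% means 0.5–1.3 expected chance responders, and 11–26% means 1.1–2.6. If a floor f applies equally in all cohorts, a true rate p is observed as p + (1 − p)f, and the gap between two doses shrinks by the factor 1 − f. As an illustration only, take true rates of 0.2 and 0.7 with f = 0.15:
- 0.2 + 0.8 × 0.15 = 0.32;
- 0.7 + 0.3 × 0.15 = 0.745;
- the gap falls from 0.50 to 0.425, and the lower rate moves most.

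**The case against.** **Size.** The documents give no within-subject CV. At 20% the effect is negligible. Closely spaced visits (Days 71, 72, 75 and 78) are not independent chances. The bleeding condition may be strict, because each ITP-BAT assessment covers the interval since the last one (SAP 7.5.2). All of this stands. Correlation and bleeding are in the ranges above; the rescue exclusion is not.

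**The 20% at 75 mg.** A reader might infer that fluctuation alone would produce the response rate expected at 75 mg. The documents do not support that. Appendix 2 says "It is assumed that the response rate at dose of 75mg, 225mg, 675mg, and 1500mg to be 0.2, 0.4, 0.55 and 0.7" as an input to the dose-selection model and does not define it as a best-over-study rate, so it is not a valid comparator.

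**Appendix 2.** A reader might also infer that the dose model is fed best-over-study response. Appendix 2 does not say so. Its non-responders are the subjects given the next higher dose, which points to status at the end of the Response Phase. Under the Protocol 3.1.1 criterion on both Day 43 and Day 50, chance response is below 1% at every CV tried. What stands is that the rule defining y is not stated.

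**Other outputs.** SAP 7.5.3 lists response category by visit and summarises the percent of visits above each platelet threshold, and SAP 7.5.4 lists duration for responders. A one-count responder would be visible there. However, the percent-of-visits summary has no doubling or bleeding condition, and none of these outputs changes the reported rate. Protocol 8.4.2 promises rates by treatment phase, which would narrow the window, but SAP 7.5.4 does not carry this over.

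**Exploratory study.** Safety is the primary objective, there is no formal hypothesis and cohorts have 10 subjects. This limits the consequence. It does not remove a bias that runs in one direction.

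**Conclusion.** The point holds in conditional form. Counting any single qualifying count over 15–17 visits, without confirmation or a control arm, inflates the R/CR rate, proportionally most where true response is low. The inflation is trivial if the within-subject CV is about 20%. It matters in cohorts of 10 if the CV is 30% or more: 5–13% of non-responders at 30% and 11–26% at 40%. These figures rest on assumed variability, correlation and bleeding frequency. That a confirmed rule cuts the floor by more than half held across the whole grid.

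The finding does not show that single-count response is a wrong definition. It is the protocol's own, so the confirmed rate belongs beside it and does not replace it.

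**What to change.** - **SAP 7.5.4 and 7.5.5:** add a confirmed response rate by treatment group, for R/CR and for clinically significant response. The criterion must be met at two assessable counts at least 7 days apart, with no failing count between them; closely spaced qualifying counts belong to one run.
- **Reporting:** show it alongside the protocol-defined single-count best response, and base efficacy and dose-response conclusions on the confirmed rate.
- **Protocol Appendix 2:** state which response rule defines y, and do not use unconfirmed best-over-study response for it.

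The cost is SAP wording, a clarifying line for Appendix 2, and programming on data already collected. Confirmed rates will be lower, and a first response at the last visit cannot be confirmed.
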